### 2 INTRODUCTION TO THE STUDY

## 2.1 Overview of Study

This will be a single-center, ambulatory, randomized, parallel group, assessor-blind, 3-week, safety study in healthy adults motivated to quit smoking. Subjects will be instructed to quit smoking (starting Day 1) and use 9 - 20 lozenges per day for 3 weeks. Subjects will be randomized 1:1 to treatment with Nicotine Bitartrate 4 mg mint lozenge (test product) or Nicorette® [Nicotine Polacrilex] 4 mg mint lozenge (reference product). In each treatment group a minimum of 10% of the study population will be smokers of  $\geq$  30 cigarettes/day, and a minimum of 40% of the study population will be smokers of 20 - 29 cigarettes/day. Randomization will be stratified by smoking status so that the treatment assignment is balanced within smoking status.

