## 4.2 Modified Intent-to-Treat (mITT) Population

The mITT population will include all subjects who were randomized and used at least 1 lozenge. This will be the main population for analysis.

17-May-2017 Final Version 1.0 Page 11 of 53

Sponsor Protocol No. 2016-NBTL-S-005

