## 7.4 Medication Administration and Treatment Compliance

Subjects will be instructed to self-administer 9-20 lozenges per day and record lozenge use through Inflamax's ePDAT take-home tablet once daily. Number of used lozenges since last visit will be calculated as deduction of the dispensed lozenge number of last visit from the

17-May-2017 Final Version 1.0 Page 16 of 53

Sponsor Protocol No. 2016-NBTL-S-005

returned lozenge number of this visit. Average number of lozenges used per day will be also calculated as dividing total number of used lozenges by total number of treatment days.

Treatment compliance will be determined by Breath Carbon Monoxide (CO) and average number of lozenges.

Breath carbon monoxide (CO) levels will be presented by subject for each visit and will be used to identify concurrent smokers. Based on level of CO, subjects will be divided as compliant subjects (CO<=10 ppm at all study day visits) and non-compliant subjects (CO>10 ppm at any study day visit). Breath carbon monoxide (CO) levels will be listed by treatment, together with visit and date. In the listing, non-compliance will be flagged. For those who comply with the requirements, CO level will be summarized with descriptive statistics (number, mean, SD, minimum, median and maximum) by treatment and visit. The number of subjects and percentage will be calculated based on whether the CO level is higher or lower than 10 ppm.

Number of lozenges will also be used to determine compliance. Lozenge use of less than 9 or more than 20 for more than 2 study days will be treated as a major violation of compliance and qualifies subjects as non-compliant.

The average number of used lozenges will be summarized with descriptive statistics (n, mean, SD, minimum, median and maximum) by treatment for the mITT population and subpopulations. The number of subjects and percentage will also be calculated based on compliance.

Compliance or non-compliance will be tabulated by treatment with frequency and percentage using the mITT population.

Medication administration will be listed by treatment, including subject number, visit, visit date, the number of dispensed lozenges, the number of returned lozenges, the number of used lozenges and average number of lozenges used per day. Non-compliance on specific day(s) will be flagged, and total number of non-compliant days will be listed.

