**Table 14.3.6.2 Summary of Study Drug Administration** 

		_	Treatment	
opulation		Statistics	Nicotine Polacrilex	Nicotine Bitartrate
Т	mITT Average number of used lozenges per day	n	xx	xx
		Mean ± SD	$xx.x \pm x.xx$	$xx.x \pm x.xx$
		Median	XX.X	XX.X
		Min, Max	xx, xx	xx, xx
	Number of non-compliance days>2 or not	n (%)		
	Yes		xx (xx.x%)	xx (xx.x%)
	No		xx (xx.x%)	xx (xx.x%)
5				
.U				

Data Source: Listing 16.2.5.2

17-May-2017 Final Version 1.0 Page 34 of 53

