**Table 14.3.6.3 Summary of Medication Compliance (mITT Population)** 

		Treatment		
Compliance	Nicotine Polacrilex n (%)	Nicotine Bitartrate n (%)		
Yes	xx (xx.x%)	xx (xx.x%)		
No	xx (xx.x%)	xx (xx.x%)		

Data Source: Listing 16.2.5.1 & Listing 16.2.5.2

17-May-2017 Final Version 1.0 Page 35 of 53

Table 14.3.7.1 Summary of difference in OMI-20 Total Score Between Day 21 and Day 24

			Treatment	
Population		Statistics	Nicotine Polacrilex	Nicotine Bitartrate
mITT	Day 21	n	xx	XX
		Mean ± SD	$xx.x \pm x.xx$	$xx.x \pm x.xx$
		Median	XX.X	xx.x
		Min, Max	xx, xx	xx, xx
	Day 24	n	xx	xx
		Mean ± SD	$xx.x \pm x.xx$	$xx.x \pm x.xx$
		Median	XX.X	xx.x
		Min, Max	xx, xx	xx, xx
	Difference between Day 21	n	xx	xx
		Mean ± SD	$xx.x \pm x.xx$	$xx.x \pm x.xx$
		Median	XX.X	xx.x
		Min, Max	xx, xx	xx, xx

PΡ

HLU

Note: OMI – Oral Mucositis Index Data Source: Listing 16.2.6.1 Similar tables as 14.3.7.1 will be generated for:

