### **Listing 16.2.5.1 Study Drug Administration**

Treatment	Subject	Visit	Dispense/ Administration Date	Number of Dispensed	Number of Returned	Number of Daily Use	Compliance Flag*	Number of Non-Compliance Days
Nicotine Polacrilex	xxxx	Day 0	DDMONYYYY	xx				
		Day 1	DDMONYYYY			XX	Yes	
		Day 7	DDMONYYYY	xx	xx	xx	No	
		Day 21	DDMONYYYY			xx	Yes	
		Day 24	DDMONYYYY		XX			xx
	xxxx	Day 0						

Note: Drug dispense happens on Day 0, 7 and 14; Drug return happens on Day 7, 14 and 24. \*Compliance will be flagged 'No' for daily lozenge use fewer than 9 or more than 20.

17-May-2017 Final Version 1.0 Page 48 of 53

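### The lozenge compliance rule ignores time on treatment, so on its plain reading a subject who leaves after one or two days cannot fail it, and drop-out of poor users raises an arm's compliance percentage

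*SAP*

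**What the plan says.** SAP 2.1 tells subjects to "use 9 - 20 lozenges per day for 3 weeks", which is 21 treatment days (Day 1 to Day 21). SAP 7.4 sets the lozenge rule: "Lozenge use of less than 9 or more than 20 for more than 2 study days will be treated as a major violation". The daily flag behind it is in the note to Listing 16.2.5.1: "Compliance will be flagged 'No' for daily lozenge use fewer than 9 or more than 20".

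SAP 7.4 then says: "Compliance or non-compliance will be tabulated by treatment with frequency and percentage using the mITT population". Under SAP 4.2, mITT takes in "all subjects who were randomized and used at least 1 lozenge", with no minimum exposure. Table 14.3.6.2 carries the Yes/No row "Number of non-compliance days>2 or not". Table 14.3.6.3 gives one overall Yes/No for compliance, drawn from the lozenge and the carbon monoxide (CO) listings together. Neither shell has a category for subjects who discontinued.

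Two things are left open. SAP 7.4 does not say whether days after withdrawal are left out or counted as use below 9. The same section also names the average number of lozenges, alongside CO, as what determines compliance, but gives no cut-off for the average and then uses the day count.

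**The concern.** Two out-of-range days are a small part of a 21-day course but all of a two-day course. A fixed count applied to everyone who took one lozenge is therefore easier to pass the sooner a subject leaves.

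This matters because the objective is to describe one lozenge relative to another and no inferential comparison is planned (SAP 6.5), so readers will set the two columns side by side. Subjects know which product they have (SAP 7.8). Early under-use followed by withdrawal is a plausible response to a lozenge that irritates the mouth. If the arms lose such subjects at different rates, the compliance percentages differ partly because of time on study, and the arm that loses more of them can look better used than it was.

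**Working it through.** The plan states no compliance figure and no sample-size calculation (SAP 3.3), so there is nothing to reproduce. The check applies the rule as written.

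**Inputs from the documents**
- Non-compliant at 3 or more out-of-range days (SAP 7.4)
- Planned treatment of 21 days (SAP 2.1)
- 50 subjects per arm (SAP 3.1)
- First on-treatment CO reading at Day 3 (SAP Table 1)

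**Assumed, because the documents give no figure**
- Daily probability *p* of out-of-range use: 0.1, 0.2 or 0.3, independent between days and the same for everyone
- Number *k* leaving after two treatment days: 0, 5 or 10 of 50

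Steps 1 to 4 count recorded on-treatment days only.

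**Step 1. What the count tolerates.** The largest share of days out of range that still passes after *d* days is min(1, 2/*d*): 100% for *d* = 1 or 2, 67% for 3, 29% for 7, 14% for 14 and 9.5% for 21. For example, 6, 5 and 9 lozenges on Days 1 to 3 average 20/3 = 6.7 per day, below the instructed range. Only two days are flagged, so the subject passes the day count.

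**Step 2. Same behaviour, different time on study.** P(pass) = P(Binomial(*d*, *p*) ≤ 2), which is 1 when *d* ≤ 2.

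| *p* | 2 days | 3 days | 7 days | 14 days | 21 days |
|---|---|---|---|---|---|
| 0.1 | 100% | 99.9% | 97.4% | 84.2% | 64.8% |
| 0.2 | 100% | 99.2% | 85.2% | 44.8% | 17.9% |
| 0.3 | 100% | 97.3% | 64.7% | 16.1% | 2.7% |

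**Step 3. Effect on an arm's percentage.** Rate = [(50 − *k*) × P(pass at 21 days) + *k*] / 50. For *p* = 0.1 and *k* = 10 this is (40 × 0.6484 + 10)/50 = 71.9%.

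| *p* | *k* = 0 | *k* = 5 | *k* = 10 |
|---|---|---|---|
| 0.1 | 64.8% | 68.4% | 71.9% |
| 0.2 | 17.9% | 26.1% | 34.3% |
| 0.3 | 2.7% | 12.4% | 22.2% |

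**Step 4. Who has to leave.** Take 40 subjects who would comply through Day 21 and 10 who are out of range every day. If all stay, the rate is 40/50 = 80%. If 5 of the 10 leave by Day 2 it is 45/50 = 90%, and if all 10 do it is 50/50 = 100%. If 5 of the 40 leave instead, they pass either way and the rate stays at 80%. The rise comes only from leavers who would have gone past two out-of-range days.

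**Step 5. The other reading.** If days after withdrawal count as zero use, a subject who leaves after Day 2 has 21 − 2 = 19 days below 9 and is non-compliant. So is anyone whose last treatment day is Day 18 or earlier, since 21 − 18 = 3. For *p* = 0.1 and *k* = 10 the rate becomes (40 × 0.6484)/50 = 51.9%, against 71.9% in Step 3. The gap between the readings is *k*/50, here 10/50 = 20 percentage points.

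**The case against.** The strongest reply is that the SAP never says an early leaver is compliant. The lozenge rule speaks of study days, while the average in the same section uses treatment days. The no-replacement rule in SAP 6.4.2 is written for study endpoints, not lozenge counts. Zero use after withdrawal would reverse the result. The sentence naming average lozenges could also make the 6.7-per-day subject non-compliant in Table 14.3.6.3. The CO part asks for 10 ppm or less at all study day visits, without saying how missed visits are treated. These points stand, and they are why the conclusion is conditional. Counting recorded days remains the plain reading, because the flag is set on daily use and no rule creates entries after withdrawal. The average has no cut-off to apply. A subject who leaves before Day 3 has no scheduled on-treatment CO to fail.

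The second reply is that other outputs show the same information: discontinuations and reasons (Table 14.1.1), discontinuation due to adverse events (Table 14.3.1.1), mean and minimum lozenges per day (Table 14.3.6.2), daily use (Listing 16.2.5.1), and the reasons for out-of-range use that the protocol's Compliance paragraph promises by group and visit. This limits the harm, but no summary table cross-classifies compliance with discontinuation.

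A reader might infer that early drop-out always raises compliance, or that the less tolerated arm will look better. The documents support neither. Step 4 shows the condition, a subject with three or more out-of-range days before leaving is correctly scored non-compliant, and no drop-out rates are given for either arm.

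**Conclusion.** The point holds in a limited form. On the plain reading, a subject with one or two treatment days cannot be non-compliant on lozenges, and the mITT compliance percentage partly reflects time on study. Drop-out of subjects who would otherwise have exceeded two out-of-range days raises their arm's percentage. Under the assumptions shown, 10 such early exits in 50 add 7.1 points at *p* = 0.1 (71.9 − 64.8) and 16.4 points at *p* = 0.2 (34.3 − 17.9). These are illustrations, not forecasts. The result also rests on days after withdrawal not being counted, which the SAP needs to state.

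It would be wrong to infer that the OMI-20 results are biased by this rule. The primary mITT summary (SAP 7.5) does not use the compliance flag, the per-protocol set requires completion (SAP 4.3), and with no inferential testing no error rate is involved. The damage is confined to the descriptive compliance tables. The change is worth making because it is cheap and removes a drop-out distortion from a by-arm comparison.

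**What to change.** In SAP 7.4 and Tables 14.3.6.2 and 14.3.6.3:

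1. Keep the existing lozenge range and two-day count for subjects who complete treatment.
2. Report subjects who discontinue before Day 21 as a separate category by arm, not as compliant. Each table then shows compliant, non-compliant and discontinued. This keeps adherence apart from completion, and avoids classifying leavers on CO visits they never had.
3. For all mITT subjects, summarise by arm the percentage of on-treatment days in range.
4. State that days after withdrawal are not counted.
5. Reconcile the sentence that bases compliance on average lozenges with the day-count rule, either by removing the average as a determinant or by saying how the two combine.

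With *p* = 0.1 and 10 of 50 leaving after two days, the arm would read 51.9% compliant, 28.1% non-compliant (40 × 0.3516/50) and 20.0% discontinued, in place of 71.9% compliant.

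The cost is SAP and shell wording. Daily use is already recorded in ePDAT and listed, so no new data are needed. The downside is that the reported compliance percentage may be slightly lower.

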## 7.5 Primary Analyses

The primary endpoint, change from baseline (Day 0) compared to each treatment study visit day (Days 3, 7, 14 and 21) in OMI-total score, will be summarized using descriptive statistics (number, mean, standard deviation, minimum, maximum, median) and presented by treatment group using mITT populations. No inferential statistical comparisons between groups will be conducted.

17-May-2017 Final Version 1.0 Page 17 of 53

Sponsor Protocol No. 2016-NBTL-S-005

## 7.6 Secondary Analyses

The primary endpoint change from baseline (Day 0) compared to each treatment study visit day (Days 3, 7, 14 and 21) in OMI-total score will be summarized using descriptive statistics (number, mean, standard deviation, minimum, maximum, median) and presented by treatment group using the PP population, HLU population, and CS population.

The change from baseline in erythema and ulcer subscores for each treatment study visit day (Days 3, 7, 14 and 21) will be summarized using descriptive statistics (number, mean, standard deviation, minimum, maximum and median) and presented by treatment group using the mITT population, PP population, HLU population, and CS population.

No inferential statistical comparisons between groups will be conducted.

## 7.7 Safety Analyses

Safety data in this study are comprised of adverse events, physical examination, vital signs and clinical laboratory assessment. All safety data will be analyzed using the mITT Population.

The continuous type safety endpoints will be summarized by treatment using descriptive statistics (n, mean, SD, median, minimum, maximum) for mITT population. The categorical type safety endpoints will be summarized by treatment using frequency and percentage for mITT population. No formal inferential tests will be performed on safety data.

#### 7.7.1 Adverse Events

Adverse events (AEs) will be coded using the Medical Dictionary for Regulatory Activities (MedDRA) Coding Dictionary version 19.1. All subjects in the mITT population will be included in the adverse event analysis. All adverse events will be listed chronologically by treatment, subject and AE start date/time. This listing will include all data collected in the eCRF, along with the derived variable duration of AE and the coded variables system organ class (SOC) and preferred term (PT).

Displays of AEs will include:

Overall Summary of AEs

This table will include the number of events, number and percent of subjects who experienced AEs, serious AEs, severe AEs, related AEs and AEs leading to study discontinuation, summarized by treatment.

17-May-2017 Final Version 1.0 Page 18 of 53

Sponsor Protocol No. 2016-NBTL-S-005

Summary of AEs by SOC, PT and Treatment

A summary of the number of events, number and percent of subjects who experienced at least one AE, as well as the number of events, number and percent of subjects who experienced each specific SOC, and PT will be presented by treatment. If a subject has more than one occurrence of the same PT then the PT will be counted only once for that subject under the SOC at which it was experienced.

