No formal statistical comparisons between treatment groups will be conducted.
For other parameters, continuous data will be summarized using descriptive statistics (mean, standard deviation, minimum, maximum, median) to aid the data interpretation at each study visit:

Adverse events and other categorical variables will be tabulated by the number and % of subjects experiencing the event by treatment group. Other indicators will include severity, seriousness and relationship to study drug by treatment group. No formal statistical comparisons between treatment groups will be conducted. Recovery will be assessed by comparing OMI-20 total score, erythema subscore, ulcer subscore and all safety endpoints on Day 24 versus Day 21.
 Compliance Breath carbon monoxide levels will be presented by subject for each visit and will be used to identify concurrent smokers (CO > 10 ppm) and to stratify results of compliant and noncompliant subjects. Average number of lozenges used per day will be tabulated. Reasons for lozenge use of < 9 or > 20 lozenges per day will be collected at each visit and presented by treatment group and by visit.

LIST OF ABBREVIATIONS AND DEFINITIONS OF TERMS

Abbreviations	Term or Definition
°C	Celsius
°F	Fahrenheit
АСТН	Adrenocorticotropic hormone
ADL	Activities of Daily Living
AE	Adverse Event
BP	Blood Pressure
CFB	Change from baseline
CFR	Code of Federal Regulations
cm	Centimeters
СО	Carbon Monoxide
CTCAE	Common Terminology Criteria for Adverse Events
DBP	Diastolic Blood Pressure
ECG	Electrocardiogram
EOT	End of Treatment
eCRF	Electronic Case Report Form
EDC	Electronic Data Capture
ePDAT®	Electronic Patient Data Acquisition Tablet
GCP	Good Clinical Practice
GSK	GlaxoSmithKline
IB	Investigators Brochure
ICF	Informed Consent Form
ICH	International Conference on Harmonization
IND	Investigational New Drug Application
IRB	Institutional Review Board
kg	Kilograms
L	Liters
mg	Milligrams
mITT	Modified-intent-to-treat
NCI	National Cancer Institute
NRT	Nicotine Replacement Therapy
OMI	Oral Mucositis Index

Randomized, Parallel Group, Assessor-Blind Comparative Study-Oral Mucosal Effects Niconovum USA, Inc.

OTC	Over the counter
рН	A measure of the acidity or alkalinity of a solution
PI	Principal Investigator
PP	Per protocol
ppm	Parts-per-million
RAISC	RAI Services Company
RAI	Reynolds American Inc.
RBC	Red blood cell count
Rx	Prescription
SAE	Serious Adverse Event
SAP	Statistical Analysis Plan
SBP	Systolic Blood Pressure

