#### 1 INTRODUCTION TO THE STATISTICAL ANALYSIS PLAN

This Statistical Analysis Plan (SAP) provides a thorough description of statistical analysis methods and presentation of the study data from the clinical trial described in Study Protocol 2016-NBTL-S-005:

"Randomized, Parallel Group, Assessor-Blind Study to Evaluate the Oral Mucosal Effects in Healthy Adult Smokers Associated with 3 Weeks of Use of Niconovum Nicotine Bitartrate 4 mg Mint Lozenge Relative to the GSK Nicorette® Nicotine Polacrilex 4 mg Mint Lozenge".

This SAP is based on the final protocol dated 27 February 2017 (Final 1.0).

The SAP includes details of data handling procedures and statistical methodology. No interim analysis is planned for this study.

The final statistical analysis will proceed according to the SAP approved by Niconovum USA, Inc. as well as by Inflamax Research. There are no deviations of analysis methods from the protocol. Any deviations in final analysis from this SAP will be documented in the final Study Summary Report.

Tables and Listings are numbered following the International Conference on Harmonization (ICH) structure E3 "Structure and Content of Clinical Study Report". All summary tables and listings will be generated using SAS® Version 9.2 or higher. Tables, listings and graphs will be delivered to the Sponsor as .rtf files.

The following documents were reviewed in preparation of the SAP:

- Electronic Case Report Form (eCRF) Final Version 1.0 dated on 20MAR2017
- Data Management Plan Final Version 1.0 dated on 03APR2017
- eCRF Completion Guidelines Final Version 1.0 dated on 20MAR2017
- Codelist Details Final Version dated on 30MAR2017

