### 2.2.2 Secondary

• To evaluate the safety and tolerability of Nicotine Bitartrate 4 mg mint lozenge and Nicorette® [Nicotine Polacrilex] 4 mg mint lozenge in this subject population.

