#### 7 STATISTICAL ANALYSES

### 7.1 Subject Disposition and Withdrawals

The following frequencies (number and percent) will be displayed by treatment group and overall for all the randomized subjects:

- Subjects in the Randomized Population (number only)
- Subjects in the Modified Intent-to-Treat Population (number only)
- Subjects in the Per-Protocol Population (number only)
- Subjects in the Heavy Lozenge Use Population (number only)
- Subjects in the Concomitant Smoker Population (number only)
- Subjects who completed the study (number and percent)
- Subjects who discontinued early, as well as reasons for subject discontinuation (number and percent)

The denominators for the percent calculations will be the number of subjects in the Randomized population per treatment or overall.

Subjects' completion/discontinuation status will be listed by treatment group and will include subject identifier, date of enrollment, date of completion/early discontinuation, date of last contact and, for those who discontinued early, the specific reason for discontinuation.

All deviations related to study inclusion or exclusion criteria, conduct of the trial, subject compliance or subject concomitant smoking will be listed. The justification of major/minor on protocol deviations may be determined among the Principal Investigator and Biostatistician from Inflamax Research, and the Sponsor.

17-May-2017 Final Version 1.0 Page 15 of 53

Sponsor Protocol No. 2016-NBTL-S-005

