## 8 TABLES, LISTINGS AND GRAPHS (TLGs) SHELLS

The following TL shells are provided as a framework for the display of data from this study. The shells may change due to unforeseen circumstances. These shells may not be reflective of every aspect of this study but are intended to show the general layout of the Tables and Listings that will be included in the final report. Table headers, variables names and footnotes will be modified as needed following data analyses.

17-May-2017 Final Version 1.0 Page 21 of 53

Table 14.1.1 Disposition of Subjects and Analysis Sets

	Nicotine Polacrilex n (%)	Nicotine Bitartrate n (%)	Overall n (%)
Number of Subjects in Randomized Population	XX	XX	XX
Number of Subjects in Modified Intent-to-Treat Population	XX	XX	XX
Number of Subjects in Per Protocol Population	XX	XX	XX
Number of Subjects in Heavy Lozenge Use Population	XX	XX	XX
Number of Subjects in Concomitant Smoker Population	XX	XX	XX
Number (%) of Subjects who Completed the Study	xx (xx.x%)	xx (xx.x%)	xx (xx.x%)
Number (%) of Subjects who Discontinued Early	xx (xx.x%)	xx (xx.x%)	xx (xx.x%)
Reasons for Early Discontinuation			
Adverse Event	xx (xx.x%)	xx (xx.x%)	xx (xx.x%)
Physician Decision	xx (xx.x%)	xx (xx.x%)	xx (xx.x%)
Protocol Deviation	xx (xx.x%)	xx (xx.x%)	xx (xx.x%)
Sponsor's Decision	xx (xx.x%)	xx (xx.x%)	xx (xx.x%)
Subject Non-compliance	xx (xx.x%)	xx (xx.x%)	xx (xx.x%)
Withdrawal by Subject	xx (xx.x%)	xx (xx.x%)	xx (xx.x%)

Note: Percentages are calculated based on the number of subjects in the Randomized Population per treatment and overall.

Data Source: Listing 16.2.1

17-May-2017 Final Version 1.0 Page 22 of 53

Table 14.1.2 Demographics and Baseline Characteristics
Modified Intent-to-Treat Population

	Nicotine Polacrilex	Nicotine Bitartrate	Overall
	(N=xx)	(N=xx)	(N=xx)
Age (years)*			
n	xx	XX	XX
Mean	xx.x	xx.x	XX.X
SD	xx.xx	xx.xx	XX.XX
Minimum	xx	xx	XX
Median	xx	xx	XX
Maximum	XX	XX	XX
Sex, n (%)			
n	xx	xx	XX
Male	xx (xx.x%)	xx (xx.x%)	xx (xx.x%)
Female	xx (xx.x%)	xx (xx.x%)	xx (xx.x%)

Note: \*Age at Informed Consent

Percentages are calculated based on the number of subjects in the ITT Population per treatment and overall.

Data Source: Listing 16.2.4.1, Listing 16.2.4.2

Programming Note: Table will also include race, ethnicity, height (cm), weight (kg), BMI (kg/m²)

17-May-2017 Final Version 1.0 Page 23 of 53

Table 14.1.3 Summary of Tobacco Use History Modified Intent-to-Treat Population

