  - Table 14.2.4.3 Summary of Change from Baseline in OMI Ulcer Score
    Heavy Lozenge Use Population
  - Table 14.2.4.4 Summary of Change from Baseline in OMI Ulcer Score Concomitant Smoker Population

17-May-2017 Final Version 1.0 Page 26 of 53

Table 14.3.1.1 Overall Summary of Treatment Emergent Adverse Events (TEAEs)

Modified Intent-to-Treat Population

	All Adverse Events		
	Nicotine Polacrilex (N=xx)	Nicotine Bitartrate (N=xx)	
Number (%) of Subjects with TEAE	xx (xx.x%) [xx]	xx (xx.x%) [xx]	
Number (%) of Subjects with Serious TEAE	xx (xx.x%) [xx]	xx (xx.x%) [xx]	
Number (%) of Subjects with Severe TEAE	xx (xx.x%) [xx]	xx (xx.x%) [xx]	
Number (%) of Subjects with Related TEAE	xx (xx.x%) [xx]	xx (xx.x%) [xx]	
Number (%) of Subjects with Study Discontinued Due to TEAE	xx (xx.x%) [xx]	xx (xx.x%) [xx]	

Note: An AE is considered to be related if it is possibly or probably related to study processes.

Summaries are presented as: number of subjects, (percentage of subjects), and [number of events].

Data Source: Listing 16.2.7

17-May-2017 Final Version 1.0 Page 27 of 53

Table 14.3.1.2 Summary of Treatment Emergent Adverse Events by System Organ Class and Preferred Term Modified Intent-to-Treat Population

	All Adverse Events		
System Organ Class/	Nicotine Polacrilex	Nicotine Bitartrate	
Preferred Term	(N=xx)	(N=xx)	
Any System Organ Class			
Any Event	xx (xx.x%) [xx]	xx (xx.x%) [xx]	
Cardiac Disorders	xx (xx.x%) [xx]	xx (xx.x%) [xx]	
Any Event	xx (xx.x%) [xx]	xx (xx.x%) [xx]	
Bradycardia	xx (xx.x%) [xx]	xx (xx.x%) [xx]	

Note: All adverse events recorded throughout the study are summarized by treatment and MedDRA System Organ Class and Preferred Term.

Summaries are presented as: number of subjects, (percentage of subjects), and [number of events]. If multiple events occur in a category, it will be counted only once for calculation of frequencies at subject level.

Data Source: Listing 16.2.7

17-May-2017 Final Version 1.0 Page 28 of 53

Table 14.3.1.3 Treatment-Emergent Adverse Events by System Organ Class, Preferred Term and Maximum Relationship (Modified Intent-to-Treat Population)

		All Adverse Events		
System Organ Class/	Maximum	Nicotine Polacrilex	Nicotine Bitartrate	
Preferred Term	Relationship	(N=xx)	(N=xx)	
ny System Organ Class				
Any Event	Unlikely	xx (xx.x%) [xx]	xx (xx.x%) [xx]	
	Possible	xx (xx.x%) [xx]	xx (xx.x%) [xx]	
	Probably	xx (xx.x%) [xx]	xx (xx.x%) [xx]	
ardiac Disorders				

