#### **Listing 16.2.7.1 Adverse Events**

Treat -ment	Subje ct	Visit	AE#	Treatment Emergent?	System Organ Class/ Preferred Term/ Verbatim Term	Start Date and Time/ Stop Date and Time/	Duration (DD:HH:M M)*	Severity/ Serious/ Relationship to study	Outcome	Action Taken/ Other Action	Caused Study Discontin -uation
Nicotin e Polacril ex	xxxx	Day 1	х	Yes	Nervous system disorders/ Headache/ Headache	DDMONYYYY HH:MM/ / Ongoing		Mild/ Yes (Death)/ Unrelated/	Recovered/ Resolved	None/None	No
			X	Yes	Gastrointestinal disorders/ Vomiting/ Vomiting	DDMONYYYY HH:MM/ DDMONYYYY HH:MM	DD:HH:MM	Moderate/ No/ Related /	Recovered/ Resolved	None/None	No

Note: \*DD: HH: MM = Days: Hours: Minutes.

Programming Note: 1) if the status of the adverse event is ongoing at the end of the study (i.e. AEONGO="Y" and AEENDTC is missing), the "Stop Date and Time" will be presented as "Ongoing"; 2) if any serious adverse event (SAE) occurs, a similar listing will be produced for SAEs separately.

17-May-2017 Final Version 1.0 Page 51 of 53

Listing 16.2.8.X Laboratory Measurements: <Laboratory Panel> Full Analysis Set Population

Treatment	Subject	Test Performed?	Date of Sample Collection	Lab Test (Unit)	Value	Reference Range Indicator	Normal Range	Clinically Significant?
	xxxx	Yes	DDMONYYYY	xxxxxx(xxxx)	XX	High	XX - XXX	No
				xxxxx (xxxx)	xx	Abnormal	Negative	
	XXXX	No						

Programming Note: < Laboratory Panel> = Hematology, Chemistry, Urinalysis. X will be assigned as 1, 2, and 3 for each laboratory panel, and each listing will continue for all parameters (unit) in that panel.

17-May-2017 Final Version 1.0 Page 52 of 53

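### No SAP summary table reports, by arm, adverse events that led to the lozenge being stopped, interrupted or reduced

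*SAP*

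**What the plan says.** The secondary objective in SAP 2.2.2 begins "To evaluate the safety and tolerability of Nicotine Bitartrate 4 mg mint lozenge" and extends to the reference lozenge.

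- **AE summary.** SAP 7.7.1 plans counts of subjects and events for all, serious and severe AEs, and closes its list with "related AEs and AEs leading to study discontinuation, summarized by treatment". The matching row in shell Table 14.3.1.1 is "Number (%) of Subjects with Study Discontinued Due to TEAE". Tables 14.3.1.2 and 14.3.1.3 break events down by organ class, preferred term and relationship.
- **Disposition.** SAP 7.1 asks for completers and for "Subjects who discontinued early, as well as reasons for subject discontinuation (number and percent"). Table 14.1.1 has "Number (%) of Subjects who Completed the Study", and no line for study-treatment status.
- **Action taken.** Listing 16.2.7.1 has a column "Action Taken/ Other Action", separate from its column for whether the event caused study discontinuation. No table uses the first of these.
- **Compliance.** SAP 7.4 treats use below 9 or above 20 a day on more than 2 study days as a major violation. Table 14.3.6.2 counts these subjects by arm, and SAP 4.3 excludes them from the per-protocol (PP) population.
- **Reasons.** The Compliance paragraph of the protocol synopsis promises a display for each visit as well as for each arm: "Reasons for lozenge use of < 9 or > 20 lozenges per day will be collected at each visit and presented by treatment group". SAP 7.4 and the shells contain no such display, although SAP section 1 states "There are no deviations of analysis methods from the protocol".

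**The concern.** Subjects set their own use within 9-20 lozenges a day. In that setting, someone who does not tolerate the product can respond by using less of it, or none, without leaving the study. Stopping or cutting the product because of an AE is a direct measure of tolerability, and a study-discontinuation row does not capture it.

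The trial is purely descriptive (SAP 6.5), so the tables are the whole result. Subjects also know which product they use (SAP 7.8), so the tendency to cut down could differ by arm. A reader comparing arms would see the events but not how often they ended or reduced exposure. Subjects off product also remain in the mITT OMI-20 summaries. That is legitimate under the mITT definition, but their number should be visible when the Day 14 and Day 21 means are read.

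**Working it through.** The plan states no figure on this point. The sample size has no formal calculation behind it (SAP 3.3); 50 + 50 = 100 is the only arithmetic to confirm. The check is therefore to follow possible subjects through the planned tables.

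**Step 1. Is staying in the study while under-using foreseen?** SAP 4.3 requires PP subjects both to complete the study and to have no major deviation, and gives under-use on more than 2 days as one such deviation. The second condition would add little if under-users always left. The plan therefore allows for completers who under-used.

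**Step 2. What would the compliance tables show?** Inputs: 21 treatment days (first lozenge on Day 1, SAP Table 1 footnote 8); a non-compliant day is use below 9 or above 20; a subject is flagged if there are more than 2 such days (SAP 7.4). The use patterns are assumed. Average = total lozenges / days.

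| Assumed pattern | Non-compliant days | Average per day over 21 days | Flagged in Table 14.3.6.2? |
|---|---|---|---|
| 12/day, stopped after Day 7 | 14 | 84/21 = 4.0 | Yes, if days after the stop count |
| 16/day, stopped after Day 7 | 14 | 112/21 = 5.3 | Yes, if days after the stop count |
| 12/day cut to 6 after Day 7 | 14 | (84 + 84)/21 = 8.0 | Yes |
| 18/day cut to 10 after Day 7 | 0 | (126 + 140)/21 = 12.7 | No |
| 12/day, stopped for the last 2 days | 2 | 228/21 = 10.9 | No (2 is not more than 2) |

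A full stop, or a cut below 9, that lasts more than 2 days normally reaches a compliance table. A cut that stays within 9-20, or a stop of at most 2 days, reaches none. No row of either compliance table carries a cause. Table 14.3.6.3 draws on the carbon monoxide listing as well, so it also mixes in smoking.

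**Step 3. Undefined denominator.** SAP 7.4 divides by treatment days without saying whether days after a permanent stop count. If they do not, the first two patterns have 0 non-compliant days and averages of 84/7 = 12.0 and 112/7 = 16.0. The second would then enter the heavy-use population (15 or more a day, SAP 4.4); at 5.3 it would not.

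**Step 4. What would an added row show?** The documents give no rate, so the counts are assumed. Exact (Clopper-Pearson) 95% intervals for one arm of 50:

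| Subjects stopping or cutting for an AE but staying | Added row | 95% interval |
|---|---|---|
| 1 | 2% | 0.1 to 10.6 |
| 2 | 4% | 0.5 to 13.7 |
| 5 | 10% | 3.3 to 21.8 |
| 10 | 20% | 10.0 to 33.7 |

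The planned study-discontinuation row counts none of these subjects in any of the four cases.

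**Step 5. Effect on the OMI-20 mean.** Assume a mean change of 1.0 in users and 0 in those who stopped. The arm mean is 1.0 × (1 − share off product): 0.96 at 4%, 0.88 at 12%, 0.80 at 20%. This shows the mechanism only; none of its inputs comes from the documents.

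**The case against.** A reader might infer that the tables count only departures from the study, so that a subject who stops the lozenge and keeps attending shows no tolerability failure anywhere. The documents do not support that. The AE is counted by arm in Tables 14.3.1.1 to 14.3.1.3, including as related or severe if so judged. Sustained use below 9 a day normally appears in Tables 14.3.6.2 and 14.3.6.3 and lowers the PP count in Table 14.1.1. OMI-20 change is also summarized in the PP population, which sets sustained under-users aside. Action taken is listed subject by subject.

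Nor do the documents say that a subject who stops the lozenge because of an AE would stay to Day 24 or be called a completer. The supplied text does not define completion, and only the protocol synopsis is available. Table 14.1.1 includes adverse event and non-compliance among the reasons for early discontinuation, so some of these subjects may be discontinued and counted there.

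Three further points are fair. Each Daily Pack holds 20 lozenges, with one pack to be used per day (SAP 2.4), so use above 20 may be uncommon and pooling it with under-use matters less than the missing cause. SAP section 8 warns that the shells may not cover everything. The Action Taken codes are not shown, so it is unverified that they distinguish stopping, interrupting and reducing.

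What stands after this: no planned table ties an AE to a change in lozenge use, some such changes reach no compliance table at all, and the protocol's reasons display is absent from the SAP text as well as from the shells.

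**Conclusion.** The point holds as a reporting gap. The SAP does not tabulate, by arm, AEs that led to the lozenge being stopped, interrupted or reduced, although tolerability is an objective and use is self-adjusted. It also omits a by-arm display that the protocol promises, while declaring no deviations from the protocol.

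The size cannot be derived from the documents. A contrast such as 6/50 = 12% against 2/50 = 4% illustrates what would not be attributed; it is not an estimate. The conclusion assumes that at least some subjects who stop or cut the lozenge remain in the study, which SAP 4.3 implies but the supplied text does not state outright. It does not extend to saying that such subjects are invisible, or that the OMI-20 means are wrong. The change is worth making as an inexpensive improvement.

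**What to change.** 1. In SAP 7.7.1 and Table 14.3.1.1, add two rows by arm: subjects with a treatment-emergent AE leading to lozenges being stopped, and subjects with one leading to lozenges being interrupted or reduced. Derive both from the Action Taken field after checking its codelist, and state what counts as reduced when use may vary from 9 to 20 a day.
2. In Table 14.1.1, add a line for subjects who permanently stopped lozenges before Day 21 but stayed in the study, taken from the daily ePDAT record and kept separate from study discontinuation.
3. In SAP 7.4, add text and a shell for the protocol's reasons for use below 9 or above 20 lozenges a day, by treatment group and visit, with the two directions shown separately. Otherwise, declare the omission as a deviation from the protocol.
4. Define completion of the study, and say whether treatment days and study days include days after a permanent stop.

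The cost is SAP wording, a few table rows, one additional display and the codelist check. The daily use, the reasons and the action taken are already planned data. No study procedure and no rule on how subjects are managed changes.
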